1 INTRODUCTION

1.1. Study Background

Periorbital Wrinkles are an early manifestation of facial wrinkles¹. They are lines or creases that form in the skin in the periorbital regions of the face. This is a significantly common multifactorial phenomenon, influenced by natural aging, photo aging (including UV exposure), facial expressions, skin type, hormonal status, genetic inclination, ethnicity, nutrition and various pathological disorders. These intrinsic factors contribute to epidermal thinning, loss of elasticity, skin fragility, etc. These are part of the human aging process, which affects the skin in its entirety and the facial skin in particular. Additional environmental factors, such as smoking, pollution and skin care, also affect periorbital wrinkles².

Wrinkles, in general, are reported to appear in people even younger than thirty years of age³. In the same manner as any other facial wrinkle, periorbital wrinkles increase gradually and affect one's appearance and facial expression. Such effect also reflects on quality of life, due to impact on social interactions, occupational functioning and self-esteem in general⁴. Therefore, periorbital wrinkle reduction treatments are sought by many worldwide.

Figure 1 - Conventional Segmentation of Periorbital Wrinkles

¹ "A Prospective Split-Face Comparative Study of Periorbital Wrinkle Treatments: Fractional Erbium Doped Yttrium Aluminum Garnet Laser Intense Pulsed Light, and Topical 0.1% Tretinoin Cream", So Eun Park, Sang Seok Kim, Chul Woo Kim, Young Her, Department of Dermatology, Kangdong Sacred Heart Hospital, Hallym University College of Medicine, Seoul,

[figure not shown]
¹Department of Dermatology, Kangwon National University Hospital, Kangwon National University School of Medicine, Chuncheon, Korea

² <https://www.mayoclinic.org/diseases-conditions/wrinkles/symptoms-causes/syc-20354927>

³ "Wrinkles", Juan Manríquez, Daniela Majerson Grinberg, and Claudia Nicklas Diaz, Clinical Evidence 2008;12:1711

⁴ Gupta MA, Gupta AK. Photodamaged skin and quality of life: reasons for therapy. J Dermatol Treat 1996;7:261–264

Figure 2 - Various Severity Levels of Periorbital "Crow's Feet" Wrinkles¹, by left-to-right, downward order of severity

1.1.1 Treatment modalities

Skin resurfacing or peel procedures have become an established non-surgical method for reducing certain skin imperfections such as wrinkles, dark spots, scars, or blemishes. Traditional fully ablative and fractional lasers are the most commonly used devices for skin resurfacing.

The skin is composed of three layers: the epidermis, the dermis, and the hypodermis. The dermis contains well-organized and oriented collagen fibers that contribute to the firmness and smoothness of the skin. As people age, these collagen fibers reduce in number and become less organized, resulting in sagging and/or wrinkled skin. When esthetic procedures are scheduled for older adults, the rate of the epidermal turnover associated with a slower wound healing and less

effective desquamation (shading of outer layers of the skin), needs to be taken into consideration⁵. In most skin resurfacing procedures, an energy source (heat, radiofrequency energy, etc.) is used to selectively damage the skin and prompt a healing response that stimulates the growth of new collagen fibers in the dermis that are well-organized. The healing response and new collagen formation results in skin that is smoother and firmer. There are numerous traditional fully ablative and fractional lasers on the market today used for skin resurfacing. Traditional and fractional lasers differ in their method of treatment. Traditional lasers have a single beam that burns or damages all of the epidermis within the treatment area of the beam. Fractional lasers divide the beam into multiple smaller beams and treat only a “fraction” of the epidermis to affect changes in the deeper epidermis or dermis. This results in multiple small cores of laser damage surrounded by areas of healthy tissue. When compared to traditional lasers, fractional lasers deliver a more superficial treatment resulting in less risk for complications and reduced time for healing. However, this also means more treatments may be required to achieve the desired results especially in areas of deep lines or wrinkles. Healing times vary by amount of treatment, but fractional laser recovery time is typically one week compared to three to four weeks for traditional lasers. In the wake of the demonstrated safety and efficacy of laser skin resurfacing, multiple additional treatment modalities have been developed for this application including the use of radiofrequency (RF) energy. The fractionated radiofrequency results in epidermal and subepidermal ablation under the conductive pins that reproduces similar effects as a fractional CO₂ laser with dermal heating, seen in the non-ablative lasers and devices⁶. The combination of epidermal ablation and dermal heating with radiofrequency, called sublative resurfacing in some studies, is suitable for skin types I–IV, for the treatment of skin laxity, wrinkles, enlarged pores, pigmented lesions, acne, telangiectasias, and scarring from trauma or acne. Subject recovery and downtime periods are significantly lower when compared with ablative laser healing times, with minimal adverse effects⁷.

1.1.2 Wrinkle Classification and Severity Assessment

Wrinkles are traditionally classified by most dermatologists into dynamic and static wrinkles.

Static wrinkles are wrinkles that are visible when the facial musculature is rested (without facial expressions), and dynamic wrinkles are those that transiently appear when facial expressions are pronounced⁸.

⁵ Ganceviciene R, Liakou A, Theodoridis A, Makrantonaki E, and Zouboulis C. Skin anti-aging strategies, Dermatoendocrinol. 2012 Jul 1; 4(3): 308–319.

⁶ Hruza G, Taub AF, Collier SL, Mulholland SR. Skin rejuvenation and wrinkle reduction using a fractional radiofrequency system. J Drugs Dermatol. 2009;8(3):259–265.

⁷ Mulholland RS, Ahn DH, Kreindel M, Paul M. Fractional Ablative Radio-Frequency Resurfacing in Asian and Caucasian Skin: A Novel Method for Deep Radiofrequency Fractional Skin

Rejuvenation. Journal of Cosmetics, Dermatological Sciences and Applications. 2012;2(3):144–150.

⁸ “Facial dynamics and emotional expressions in facial aging treatments”, [name],¹ [name],² & [name]^{2,1} Private Practice, Mulhouse, France ² Private Practice, Toulouse, France, Journal of Cosmetic Dermatology, 0, 1–13

1.1.3 Fitzpatrick Wrinkle Classification Scale (FWCS)

Facial wrinkles are conventionally classified according to Fitzpatrick's classification scale for facial wrinkles, described in the following Table 1^{9,10,11}:

Table 1 - The Fitzpatrick Periorbital and Perioral Wrinkle Classification

Class	Description	Score	Description
I	Fine wrinkles	1-3	Mild: Fine texture changes with subtly accentuated skin lines.
II	Fine to moderate depth wrinkles, Moderate number of lines	4-6	Moderate: Distinct papular elastosis (individual papules with yellow translucency under direct lighting) and dyschromia
III	Fine to deep wrinkles, numerous lines, with or without redundant skin folds	7-9	Severe: Multipapular and confluent elastosis (thickened, yellow, and pallid) approaching or consistent with cutis rhomboidalis.

⁹ "Pulsed carbon dioxide laser resurfacing of photo-aged facial skin", Fitzpatrick, R. E., Goldman M. P., Satur, N. M., and Tope, W. D. Arch. Dermatol. 132: 395, 1996.

¹⁰ A Fractional Bipolar Radiofrequency Device Combined with a Bipolar Radiofrequency and Infrared Light Treatment for Improvement in Facial Wrinkles and Overall Skin Tone and Texture. Gold AH, et al. Aesthet Surg J. 2016.

¹¹ <https://www.ncbi.nlm.nih.gov/pmc/articles/PMC3713733/> Fractionated microneedle radiofrequency for the treatment of periorbital wrinkles. Kim JK, et al. J Dermatol. 2013

1.2. Study Rationale

All current technologies available in worldwide markets nowadays do not offer full permanent clearance of periorbital wrinkles and cause certain levels of discomfort to the patients, accompanied with varying durations of downtime. Appearance is often improved to some degree of satisfaction of the subject, but not to the extent of complete solution for the condition. Due to the psychological impact of the conditions and its negative effect on life quality, better modalities are always sought. The Tixel technology aims to offer a more user friendly, radiation free, safety googles free, anesthesia/analgesia free at low device settings, toxic fumes free, safe and efficacious modality for fractional skin resurfacing of periorbital wrinkles, with results similar or better to currently market-available devices in the US¹².

1.3. Study Device Description-The Tixel system

[figure not shown]
The Tixel family of products (for example Tixel 2 as in Figure 3) employs a thermo-mechanical technology that has been designed to provide a comparable clinical effect as a pulsed non-ablative laser and surface RF devices, which can be used as a treatment modality for a variety of dermal applications. The Tixel technology is based on the supply of contact-transferred heat from a high temperature (385°- 405°C) metal element (called a “tip”) consisting of an array of miniature pyramids. The tip (see Figure 4 and Figure 5) generates thermal coagulation in the tissue (usually 200-300 microns deep) within 5 – 18 milliseconds pulse duration (contact duration between the tip and the skin), thus mimicking pulsed laser or surface RF action.

The device has been cleared for marketing in multiple countries including European Union (EU), Australia, South Korea, Taiwan, Israel and other.

Figure 3 - The Tixel 2 Device

[figure not shown]

Figure 4 - The Tixel Standard Tip

¹² https://www.accessdata.fda.gov/cdrh_docs/pdf15/K150409.pdf

Figure 5 - The Tixel Small Tip

1.3.1. Safety Features of the Tixel

The device is fully IEC-60601 compliant (safety and EMC).

Over 750 Tixel devices have been sold to dermatologists and aesthetic doctors in the past 5 years, in over 25 countries.

The Tixel device is designed with core safety, which is ensured via several aspects of its components:

1. The device has an over-temperature automatic thermal shutdown in case of undesired temperature rise. This component is strictly hardware based.
2. In case of a power fail, the Tip will always be retracted backwards to its home position detached from the skin.
3. The system is always in a rested (home) position and activated only when the trigger is pressed.
4. An air-cooled system for handpiece cooling which does not contain any type of liquid.
5. Mechanical BIT (Built-In Test) – Before commencing operation mode, the system verifies free motion of the mechanical system.

1.3.2. Expected Possible Side Effects

In the same manner as all fractional skin treatment devices, there is risk of: Temporary swelling; Skin redness; Pain and/or burning sensation; Forming of large scabs or scabs lasting more than 15 days; Significant/thick skin peeling; Post Inflammatory Hyperpigmentation (PIH); Hypopigmentation; Sensitivity to sun exposure; Local burns; Scars, edema, erythema and watery eye for few hours after the treatment.

1.3.3. Benefits

A possible benefit of using Tixel is the potential for improvement in wrinkle severity. Additional potential benefits of improving the appearance of wrinkles could include enhanced well-being, with improved satisfaction with the appearance of less peri-orbital wrinkles or the perception of a having a more youthful appearance.

1.3.4. Intended Use and Indications for Use

Skin rejuvenation by fractional non-ablative treatment of the skin.

The Tixel System is intended for cutaneous procedures requiring coagulation of soft tissue and skin resurfacing procedures. Treatments are performed by physicians and trained clinicians.

1.4. Study Objective

To demonstrate the safety and performance of the Tixel fractional system for treatment of periorbital wrinkles.

1.5. Study Design

A Prospective, Multicenter, Single-Arm Clinical Study of 51 subjects who are seeking a procedure to reduce the appearance of the periorbital wrinkles, and meet study eligibility criteria, and have provided informed consent will be enrolled in the study. Up to 5 investigational centers in Israel and the United States will participate in the recruitment. Each study subject will receive **four treatments** with Tixel 2 in a monthly interval. Follow-up will occur at 1 month and 3 months following the last treatment.

1.6. Treatment parameters in the study and treatment area:

1. Protrusion- between 400-600 microns,
2. Pulse duration- between 10-12 milliseconds (lower for skin-type V e.g. 6-8).
3. Single or double pass, except crow's feet which can be treated in crisscross when severe wrinkles exist.
4. The treated area outside of the orbital rim should encompass below and above the brow, lower eyelid and at beyond (1-2 cm at 45 degrees above and below) the most lateral aspect of the most lateral wrinkle.
5. Treatment directly on the eyelid is forbidden.

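### Section 1.6 lists the lower eyelid in the area, outside the orbital rim, that treatment should cover, then bans treatment directly on the eyelid, and no visible text reconciles the two

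*Combined protocol and SAP*

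**What the plan says.** Section 1.6 sets the treatment parameters and the treatment area in a list of five items. Two of them bear on the eyelid.

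- Item 4: "The treated area outside of the orbital rim should encompass below and above the brow, lower eyelid and at beyond" the most lateral wrinkle, with a margin of 1-2 cm given in brackets.
- Item 5: "Treatment directly on the eyelid is forbidden".

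Item 2 of the same list sets the pulse duration at 10-12 ms, lower for skin type V, with 6-8 ms as the example.

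Other sections give the setting in which these items are applied:

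- Section 1.3 describes the device as working by "contact-transferred heat from a high temperature (385°- 405°C) metal element".
- Section 1.3.2 lists among the expected possible side effects "Local burns; Scars, edema, erythema and watery eye for few hours after the treatment".
- Section 1.3.4: "Treatments are performed by physicians and trained clinicians".
- Section 1.5: "Up to 5 investigational centers in Israel and the United States will participate in the recruitment", and "Each study subject will receive four treatments with Tixel 2 in a monthly interval".

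**The concern.** Item 4 names the lower eyelid as a site that treatment should take in. Item 5, directly after it, rules out treatment on the eyelid with no exception. An operator who gives the term lower eyelid its ordinary meaning cannot follow both.

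What is at stake is a safety boundary. The two items together tell the operator how close to the eye a very hot contact tip may be applied. Safety is part of the study objective (section 1.4), and related adverse events are the primary safety variable (section 1.7.3). With physicians and trained clinicians treating at up to 5 centers in two countries, the limit should be one that everyone can apply in the same way without having to interpret it.

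**Working it through.** There is no figure in the plan to reproduce on this point. The check is a comparison of texts.

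**1. The two items side by side**

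| | Item 4 | Item 5 |
|---|---|---|
| Function | Describes the area to be treated | Prohibits treatment |
| Lower eyelid | Named among the sites to be covered | Not named separately; falls within the general term eyelid |
| Upper eyelid | Not named | Falls within the general term eyelid |
| Qualifier | Area is introduced as outside the orbital rim | Applies to treatment directly on the lid |
| Exception | None stated | None stated |

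Taken at their words, the items overlap at the lower lid: one includes it, the other forbids it.

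**2. Can both be met?** Two routes are open.

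- The qualifier about the orbital rim may govern the whole list in item 4. The lower eyelid would then stand for skin outside the rim, next to or below the lid.
- The word below in item 4 may carry over to the lower eyelid, so that the skin below the lid is meant.

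Both are inferences. The grammar of item 4 is broken, and it does not settle which words the qualifier or the preposition governs.

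**3. Does another passage settle it?** The word eyelid occurs three times in the visible text: in items 4 and 5, and in exclusion criterion 6a, which concerns earlier cosmetic procedures and does not define the treated area. Inclusion criterion 4, exclusion criteria 7, 8 and 10, the photography row of Table 2, and section 4.4 (GAIS) all refer to a treated area, treatment area or treatment sites. None gives its boundary at the lower lid.

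**4. What could not be checked.** Exclusion criterion 2 refers to the User Manual and the Instructions for Use, but for contraindications; section 1.6 does not refer to them for the treated area. Their text is not part of the documents, and the figures are not shown. Any of these may define the area.

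**5. Which device settings apply.** Section 1.3 says that the tip "generates thermal coagulation in the tissue (usually 200-300 microns deep) within 5 – 18 milliseconds pulse duration". That is the range for the product family. The settings for this study are those of section 1.6 item 2: 10-12 ms, for example 6-8 ms for skin type V. The tip temperature of 385-405°C comes from section 1.3; section 1.6 gives no separate value.

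**The case against.** The strongest reply is that this is loose drafting in one sentence, not a pair of opposed orders. Item 4 describes an area that is by its own terms outside the orbital rim. Item 5 follows at once, and it is short and absolute. A general description followed by an express ban can be read as an area with a carve-out. On that reading nothing permits treatment on the lid, and all that is unclear is where the treated area ends near the lower lid. The manual or a figure may show even that.

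Much of this stands. The compatible reading is available, and the unseen sources limit what can be said about the instructions operators actually receive. It does not remove the point, because the protocol leaves the operator to infer the reading, and a boundary near the eye should be stated.

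Four stronger readings are tempting, and the documents do not support them:

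- **The protocol instructs treatment on the lid.** It does not say so expressly, and the orbital rim qualifier and item 5 both point away from that reading.
- **Sites will treat different areas.** This is a risk. Nothing in the documents shows that it happens.
- **Every session is affected.** The plan allows up to 51 × 4 = 204 treatment sessions. That is the number governed by section 1.6, and any wording there would govern the same number. It is not a count of sessions treated differently.
- **The analysis is compromised.** Section 6.2.2 leaves major deviations to an independent reviewer but does not mention treatment-area deviations, so a consequence for the per protocol set is conditional at most.

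**Conclusion.** The point holds as an internal inconsistency in a safety instruction that should be fixed. Items 4 and 5 of section 1.6 cannot both be followed literally, and no visible passage says how to read them together. Confidence is high that the visible text contains no reconciling statement. It is lower that operators lack such a statement altogether, because the User Manual, the Instructions for Use and the figures were not available.

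The size cannot be put as a number: the documents do not allow an estimate of how many sessions or subjects would be treated differently. No effect on the primary result or the sample size is claimed. The weight of the point rests on the hazard, which is contact heat near the eye, and on the number of centers that must apply the boundary in the same way.

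**What to change.** The sponsor and investigators should reconcile items 4 and 5 into one statement of the treated area and the prohibited area, without overlap between them, and with the upper and the lower lid each addressed. If the User Manual, the Instructions for Use or a figure already defines the areas, section 1.6 should cite it. The sites should then be told. Which area is correct is for the sponsor and investigators to decide; this review takes no position on it.

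The cost is a protocol clarification and a site memo, with no added procedures.

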1.7. Study Endpoints

1.7.1. Primary Efficacy Endpoint

Comparison of the proportion of subjects with a ≥ 1 -score improvement on the FWCS at the 3-month visit compared to baseline as determined by at least 2 out of 3 blinded Independent Photographic Reviewers.

The study design assumes a 65% success rate of subjects with a ≥ 1 -score change on the FWCS, therefore, greater or equal to 65% of subjects must be rated with a ≥ 1 -score improvement 3 months after treatment and must be statistically significantly.

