6.1. Determination of Sample Size

- The objective of this study is to demonstrate that study participants positively respond to the Tixel, thus the primary endpoint will be assessed via the percentage of study participants that demonstrated an improvement in the FWCS from baseline to the 3-month visit.
- An improvement is clinically important when FWCS ≥ 1 score.

The sample size calculation is based on the rate of subjects for which a score improvement on the FWCS at 3-month compared to baseline (success rate). The success rate is expected to be 65%.

When the sample size is 44, a two-sided 95% confidence interval for a single proportion using the large sample normal approximation will extend 0.14 from the observed proportion for an expected proportion of 0.65.

To account for possible missing data (up to 15% attrition), 51 subjects will be enrolled.

- Total N: up to 51 study participants

A study investigating the effects of RF device on the improvement of appearance of peri-orbital wrinkles (VIVACE K150409 Class II FDA approved device) utilized a FWCS cutoff as 60%, supporting this value in the present sample size computation.

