6.3. Endpoints for Analysis

6.3.1. Primary Efficacy Endpoint

The primary efficacy endpoint is the comparison of the proportion of subjects (i.e. percentage of treatment responders) with a ≥ 1 -score improvement on the FWCS at the 3- month visit, as compared to baseline as determined by at least 2 out of 3 blinded Independent Photographic Reviewers. The study design assumes a 65% success rate of subjects with treated wrinkles with a ≥ 1 -score change on the FWCS; therefore, even or greater than 65% of subjects must be rated with a ≥ 1 -score improvement 3 months after treatment. and must be statistically significantly.

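### Primary success must be statistically significant, but the single-arm plan names no reference proportion and declares no test; with its own 60% and 65%, 33 to 35 responders of 44 pass or fail by a later choice

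*Combined protocol and SAP*

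**What the plan says.** Section 1.5 describes "A Prospective, Multicenter, Single-Arm Clinical Study of 51 subjects", so there is no concurrent control.

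The primary success rule appears twice. Section 1.7.1 requires that at least "65% of subjects must be rated with a ≥ 1 -score improvement 3 months after treatment and must be statistically significantly". Section 6.3.1 says that "even or greater than 65% of subjects must be rated" as improved at 3 months, then adds "and must be statistically significantly". Neither section says what the proportion is to be tested against, by which test, or at which level.

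Section 6.1 plans on an expected success rate of 65%. It justifies the size by precision: by the normal approximation, the two-sided 95% interval at 44 subjects "will extend 0.14 from the observed proportion for an expected proportion of 0.65". It also reports that a study of another device "utilized a FWCS cutoff as 60%, supporting this value in the present sample size computation".

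Section 6.2.2 places the primary analysis on the per-protocol set. Section 6.4.3 lists an MMRM among its methods for missing wrinkle scores. Section 4.3 gives a further definition of subject success, which adds correct identification of the 3-month images by at least two of the three raters.

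**The concern.** In a single-arm trial, significance of a proportion has meaning only against a stated value. The comparison with baseline does not supply one, because improvement from baseline is already part of each subject's responder status. The interval in 6.1 is offered for precision and is not declared as the decision rule. The 60% in 6.1 is cited in support of a planning value and is not named as a performance goal. The MMRM in 6.4.3 contains no reference proportion.

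The reference and the interval method could therefore be chosen once results are known. The opening of section 6 allows alternative or additional analyses before database close, and investigators score FWCS and GAIS openly at both follow-up visits. What is at stake is the pass or fail verdict on the primary endpoint: sensible ways of filling the gap give opposite answers on the same data.

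**Working it through.** **Inputs.** Evaluable n = 44, expected rate 0.65, two-sided 95% normal-approximation interval and the cited 60% (all 6.1); the 65% hurdle (1.7.1, 6.3.1). References of 50% and 55% are assumptions that do not stand in the documents. The two-sided 5% level is inferred from the 95% interval in 6.1.

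**1. The plan's own figure.** Half-width = 1.96 × √(0.65 × 0.35 / 44) = 0.141, which reproduces the stated 0.14.

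**2. The 65% hurdle.** 0.65 × 44 = 28.6, so 29 responders are needed (28/44 = 63.6%; 29/44 = 65.9%).

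**3. Lower 95% limits at n = 44.** Normal approximation: p̂ − 1.96 × √(p̂(1 − p̂)/44). Exact: Clopper-Pearson.

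| Responders | Observed | Normal approx. | Exact |
|---|---|---|---|
| 28 | 0.636 | 0.494 | 0.478 |
| 29 | 0.659 | 0.519 | 0.501 |
| 31 | 0.705 | 0.570 | 0.548 |
| 32 | 0.727 | 0.596 | 0.572 |
| 33 | 0.750 | 0.622 | 0.597 |
| 34 | 0.773 | 0.649 | 0.622 |
| 35 | 0.795 | 0.676 | 0.647 |
| 36 | 0.818 | 0.704 | 0.673 |

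**4. Smallest passing count, and P(pass) at a true 65%.** The count must meet the hurdle and have its lower limit above the reference. P(pass) is the binomial tail P(X ≥ count | 44, 0.65).

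| Reference | Source | Count, normal / exact | P(pass), normal / exact |
|---|---|---|---|
| 50% | assumed | 29 / 29 | 0.52 / 0.52 |
| 55% | assumed | 31 / 32 | 0.28 / 0.18 |
| 60% | cited in 6.1 | 33 / 34 | 0.11 / 0.06 |
| 65% | hurdle and planning value | 35 / 36 | 0.03 / 0.01 |

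**5. Undecided counts.** With the documents' 60% and 65% only, 32 or fewer fail and 36 or more pass whatever is chosen; 33, 34 and 35 are undecided. If 50% is also allowed, 28 or fewer still fail and 29 to 35 are undecided.

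| True rate | P(33 to 35) | P(29 to 35) |
|---|---|---|
| 65% | 0.10 | 0.51 |
| 70% | 0.24 | 0.72 |
| 75% | 0.39 | 0.74 |
| 80% | 0.38 | 0.52 |
| 85% | 0.18 | 0.21 |

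**6. Reference or method?** With the reference fixed, the choice between these two intervals changes the verdict at only three counts: 31 (against 55%), 33 (against 60%) and 35 (against 65%). The rest turns on the reference.

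**7. Sensitivity to n.** 15% attrition from 51 leaves 51 × 0.85 = 43.35. At n = 43 the hurdle needs 28, a limit above 60% needs 32 or 33, and a limit above 65% needs 34 or 35. The pattern is unchanged.

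**The case against.** The clause can be read so that it does little. If significance means better than chance or any improvement over baseline, a reference near 50% is natural. Under 4.3, three raters each guessing independently at one half would reach two or more correct identifications with probability 3 × 0.125 + 0.125 = 0.50, and also requiring a score change cannot raise that. Against 50% at n = 44, both intervals are satisfied at 29 responders, so the 65% hurdle alone binds. This stands as a possible reading. It shows that the effect could be nil, but the documents do not adopt it.

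It can also be said that 6.1 names only one interval method for this proportion. That stands too: carrying the normal approximation into the analysis would settle the method. It would leave the reference open, and the reference does most of the work.

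A reader might infer that the plan itself leaves 29 to 35 responders undecided. The documents do not support that as the main figure: the wider range depends on a 50% reference that they do not contain. A reader might also take 60% as the performance goal. The wording in 6.1 ties it to the sample size computation, and it can equally be read as support for the expected rate.

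**Conclusion.** The concern holds as an ambiguity in the pass or fail rule, and it must be fixed. No reference proportion is given and no test is declared, so at 44 evaluable subjects and with the documents' own percentages, 33 to 35 responders pass or fail by a later choice. The probability of landing there ranges from 0.10 to 0.39 over true rates of 65% to 85%. The wider range of 29 to 35 applies only if a 50% reference is admitted. At the assumed 65%, the chance of success is 52% against 50%, 6 to 11% against 60% and 1 to 3% against 65%. The last figure makes 65% hard to reconcile with the planning value if it is meant as the reference.

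Two stronger conclusions might be drawn and are not supported. One is that the primary rule cannot be applied at all: the 65% hurdle is computable, and under one reading the significance clause adds nothing to it at n = 44. The other is that the sample size is miscalculated: the stated precision reproduces, and 6.1 claims no power.

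These results assume 44 evaluable subjects, a two-sided 5% level and independent binomial outcomes.

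**What to change.** Before any outcome data are reviewed, including the investigators' unblinded FWCS and GAIS scores:

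- In 1.7.1 and 6.3.1, state one performance goal with its justification and one interval method, and define significance as the lower limit of the two-sided 95% interval exceeding that goal. The normal approximation is already named in 6.1; an exact interval is the conservative alternative.
- In 6.1, say whether 60% is that goal or only support for the expected rate, and give the required responder count. As illustrations at n = 44, a 60% goal needs 33 (normal approximation) or 34 (exact).
- Make the responder definition in 4.3 agree with 1.7.1 and 6.3.1. Section 4.3 adds correct image identification and states its FWCS condition as a score of at least 1, not an improvement of at least 1. Until these agree, a goal and an interval alone do not make the verdict determinate.

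Optional: keep 65% as a planning assumption only, or state in 6.1 that as a hurdle it caps the chance of success at about 52% at n = 44 if the true rate is 65%.

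The cost is wording, plus openly stating a low probability of success at the assumed rate. The change makes the rule definite but does not raise that probability. No extra patients are needed.
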